3. STUDY DESIGN

We will use a stepped-wedge randomised controlled trial (RCT) design (Hemming, Haines, Chilton, Girling, & Lilford, 2015). This design involves random and sequential crossover of groups from control to intervention until all groups are exposed to the intervention. A stepped wedge cluster RCT is especially useful when the intervention is thought to do more good than harm (i.e., when there is no equipoise). In that situation, it is unethical to withhold or withdraw the intervention from a proportion of the subjects as would occur in a parallel group or classic cluster RCT. Besides, it may be impossible to implement the intervention in half of all clusters simultaneously because of practical, logistical, or financial reasons, which is also the case in the current study with regard to the practical and logistical reasons. Then, the stepwise treatment implementation of the stepped wedge design offers a solution. Since all patients included in this study will be offered the intervention, which may contribute to limiting lost to follow-up

The personalized approach, local collaborations with the social domain and organizational differences between general practices will result in nuanced differences in how our intervention will be applied. Besides, training the Positive Health methodology and the enhanced collaboration between domains most likely effects patients not-offered the intervention as well. Randomisation will therefore be done by cluster.

This study will be performed in 20 general practices. Each practice will form one cluster. We aim to include an average of 10 patients per cluster. A GP or POH-GGZ can only participate in one cluster. The terms GP practice and cluster will be used alternatively and exchangeable from this point on, both referring to the given description.

Each participating patient starts with a control period and will cross-over to the intervention period. The control period varies between 2 to 8 months. All patients from a GP practice cross-over at the same moment. Therefore the GP-practices are randomized into one of four groups.

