4.4 Sample size calculation

Sample size calculation for a stepped wedge cluster RCT is performed using the formule of De Hoop et al (Woertman et al., 2013). The unadjusted sample size for a RCT was established on 380, 190 per arm, based on average one year Health Insurance Act spending of a mean of ca €22.494 (€24.585SD)(source Statistics Netherlands), with 80% power, 5% alpha, 2-sided Equality and 25% decrease. The design effect for this study is 0.54. This is based on 1 baseline measure, 4 steps, and ICC of 0.1, 10 patients per cluster and a lost to follow-up of 20%. This leads to a sample side of 204 patients. Rounded off, we will include 200 patients divided over 20 clusters.

TREATMENT OF SUBJECTS

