6. STATISTICAL ANALYSIS

Before analysis, all data will be cleaned improving data quality.

Quantitative data:

We will conduct intention-to-treat and per protocol analysis. We will use multilevel generalized linear models with the patient as the first level to correct for the repeated measures. The GP-practice (or cluster) will be the second level, and the group in which the GP practice is randomized will be the third level. We will adjust for level of integration, neighbourhood, time from start of study (continuous; with an interaction between cluster and time so that each cluster had its own underlying time trend), and total time on the randomised intervention, with time before intervention given as zero (continuous). Based on ICPC-codes used to select eligible patients, we will explore if subgroups can be identified in mainly (chronic) somatic, mainly mental or mainly social problems. Furthermore, analyses/ results will be stratification for sex. The analysis of the implementation will be descriptive.

Cost-effectiveness analysis/budget impact analysis:

The economic evaluation will consist of a trial-based cost-utility analysis (cost per QALY) with a time horizon of one year and a cost-utility analysis with a lifetime horizon (cost per QALY). Both analyses will be performed from a societal perspective. Next to this a Budget Impact Analysis will be performed according to the ISPOR Task Force principles.

Qualitative data:

Qualitative data will be collected through interviews or focus groups with care providers and patients and audiorecording. The interviews and focus groups will be conducted using a topic list based on experience of the pilot (protocol number **NL8223-10216**) and literature, to determine their satisfaction with the new approach.

The collected qualitative data will be analysed using both an inductive and deductive approach. This will be done by first transcribing the data and doing a thematic content analysis. After this, the data will be put into an initial coding book and further analysed until a final coding book is formed. The deductive analysis will be done using the positive health methodology. We will analyze whether positive health topics and techniques are being discussed and applied, as recommended by the methodology.

The audiotapes will be scored by two independent observers using the validated OPTION5 questionnaire.

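### The design effect of 0.54 in 4.4 belongs to a design with new patients at every step, not to the closed cohort that is followed and modelled; the direction of the error depends on correlations the protocol does not state

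*Protocol*

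**What the plan says.** Section 4.4 starts from an individually randomised trial: "The unadjusted sample size for a RCT was established on 380, 190 per arm". The basis is one-year spending with a "mean of ca €22.494 (€24.585SD") and is sized "with 80% power, 5% alpha, 2-sided Equality and 25% decrease". It then applies a stepped-wedge design effect: "The design effect for this study is 0.54. This is based on 1 baseline measure, 4 steps, and ICC of 0.1", with "10 patients per cluster and a lost to follow-up of 20"%. The result is 204, rounded to 200 patients in 20 practices. The only correlation listed is the practice ICC.

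Elsewhere the protocol describes repeated observation of the same people. Section 3: "Each participating patient starts with a control period and will cross-over to the intervention period". Section 5.5 rules out replacing patients who withdraw. Section 5.1.1 plans 7 or 8 completions of the cost and EQ-5D questionnaires per participant. Section 6: "We will use multilevel generalized linear models with the patient as the first level to correct for the repeated measures".

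**The concern.** In a closed-cohort stepped wedge, each patient supplies both control and intervention observations, so the within-patient comparison is a main source of information. A design effect built from a practice ICC alone has no place for it. Section 6 recognises the patient level and 4.4 leaves it out, so the structure sized is not the structure run or analysed.

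At stake is whether the stated 204 patients and 80% power mean anything for this trial. The point also bears on any repair of 4.4: correcting the other inputs while keeping 0.54 would give another figure for the wrong design.

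**Working it through.** **Inputs from 4.4.** 20 practices, 10 patients each, 4 steps, 1 baseline (5 measurement rounds), ICC 0.1, unadjusted N of 380, mean 22,494, SD 24,585, 25% decrease, two-sided 5%. The protocol gives no within-patient correlation and no practice autocorrelation; every value of these below is an assumption.

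**Reproducing 0.54.** The single-ICC stepped-wedge formula with k = 4 steps, b = 1 baseline, t = 1 measurement per step, n = 10 and ρ = 0.1 is

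DE = [1 + ρ(ktn + bn − 1)] / [1 + ρ(ktn/2 + bn − 1)] × 3(1 − ρ) / [2t(k − 1/k)]

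= (1 + 0.1 × 49)/(1 + 0.1 × 29) × 2.7/7.5 = (5.9/3.9) × 0.36 = 0.5446.

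Then 380 × 0.54 = 205 and 380 × 0.5446 = 207, both close to the stated 204.

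**What 0.54 assumes.** I computed the generalised-least-squares variance of an on/off effect for 4 sequences of 5 practices over 5 rounds, with fixed period effects and total variance 1. The practice variance is 0.1, the patient variance 0.9r and the residual 0.9(1 − r). Here r is the correlation of a patient's repeated values beyond the practice, constant over time. DE = variance/(4/200). At r = 0 this gives 0.5446 exactly. So 0.54 is the value for observations that are independent given the practice, as if new patients were measured at each round.

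**Adding the patient level (exchangeable, constant effect).** Power = Φ(d/SE − 1.96). Two effects are shown:
- d = 0.287, the effect that 380 patients detect with 80% power: 2.8016 × √(4/380).
- d = 0.229, the stated decrease: 0.25 × 22,494/24,585 = 5,623.5/24,585.

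| r (assumed) | SE, 200 patients | DE | 380 × DE | Power d = 0.287, 200 patients | Power d = 0.229, 200 patients | Power d = 0.229, 160 patients |
|---|---|---|---|---|---|---|
| 0 | 0.1044 | 0.545 | 207 | 79% | 59% | 51% |
| 0.3 | 0.0890 | 0.396 | 151 | 90% | 73% | 64% |
| 0.5 | 0.0760 | 0.289 | 110 | 97% | 85% | 77% |
| 0.7 | 0.0594 | 0.176 | 67 | 99.8% | 97% | 93% |

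The 160 patients are 8 per practice after the 20% loss. If the patient correlation instead decays geometrically at 0.5 per step, DE is 0.338 and power for d = 0.229 with 200 patients is 79%.

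**Is the direction stable?** Starting from r = 0.5 (DE 0.289) and changing one assumption at a time:

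| Change | DE |
|---|---|
| Practice autocorrelation 0.8 instead of 1 | 0.41 |
| Practice autocorrelation 0.5 instead of 1 | 0.57 |
| Practice-specific time trends plus time on intervention, linear time | 0.40 |
| Same two terms, period effects kept | 0.70 |

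The last two rows read Section 6 as an on/off effect plus both adjustment terms, with the practice slopes fixed. Either term without the other leaves DE at about 0.30 to 0.33. With SE = √(0.02 × DE), DE 0.57 gives SE 0.107 and power 77% for d = 0.287; DE 0.70 gives SE 0.118 and power 68%.

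**Limits of the check.** It uses the 5 rounds implied by 4.4, not the 7 or 8 measurements planned.

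**The case against.** The strongest reply is that the omission is harmless. The arithmetic of 0.54 is right, the formula is a published one, and with the protocol's own 380 and a simple cohort model the trial has more power than stated. Nobody need recruit another patient. Much of this stands: the fault is the choice of formula, not a slip in computing it, and it gives no ground for changing N.

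Two further objections also stand. The documents give no source for any value of r. And a replacement that adds only a patient level still does not match Section 6, which also plans practice-specific time trends and a time-on-intervention term. With both, or with imperfect practice autocorrelation, much or all of the gain can disappear. Swapping 0.54 for 0.29 could therefore print an over-optimistic power.

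This limits the size and the remedy; it does not remove the point. A zero within-patient correlation beyond the practice is still assumed without being stated, and it contradicts the reason Section 6 gives for its patient level.

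A reader might infer that the omission decides whether the trial reaches 80% power, since power for the stated 25% decrease goes from 59% at r = 0 to 85% at r = 0.5. The documents do not support that reading. The 59% arises from a separate fault: the stated mean, SD and decrease require 301 per arm by the two-sample formula, not 190. On the protocol's own 380 the same step is from 79% to 97%.

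**Conclusion.** The point holds as a mismatch between sections 3, 5.1.1, 5.5 and 6 on one side and 4.4 on the other. The 0.54, the 204 and the 80% describe a design with different patients at each step.

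For an exchangeable correlation and a constant on/off effect, the error is conservative: DE is 0.40 to 0.18 for r from 0.3 to 0.7, and power is 90% to 99.8% against 79% on the protocol's own 380. Under weaker practice autocorrelation or the fuller Section 6 model, DE at r = 0.5 runs from 0.40 to 0.70, which spans 0.54.

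Two stronger readings are therefore unsupported: that the omission leaves the trial underpowered, and that 110 or fewer patients would do. Each needs a correlation structure that the protocol does not state. What can be said is that the stated power is not established for this design. This should be corrected because 4.4 fixes the figure and the correction is cheap.

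**What to change.** In 4.4, replace 0.54 with a closed-cohort stepped-wedge calculation that follows the Section 6 model (patient level, time terms and the way the intervention effect enters) and the actual measurement schedule. State the within-patient correlation and the practice autocorrelation as assumed ranges, for example r from 0.3 to 0.7 and autocorrelation from 0.5 to 1. Prior CBS costs may inform these only if they are available for periods matching the two-month steps; a correlation between yearly totals is not the same quantity.

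Restate the power that 200 patients, and 160 after 20% loss, give for the 25% decrease. Do this together with the correction of the 380, since repairing either alone leaves a wrong figure. Keep the number of patients unchanged.

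The cost is a recalculation and a rewritten paragraph, with no extra patients or data. The small downside is that more assumed parameters appear, shown as ranges.

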4.5 Investigational treatment

The proactive integrated care intervention that will be used consists of five steps:

1. Active invitation of the patient from the practice

2. Consult of 45 minutes with a trained Practice Nurse Mental Health Care based on the Positive Health Methodology. The outcome of this consultation is a spiderweb with an overview of current health status according to positive health methodology.
3. Multidisciplinary Team meeting (MDO) based on the spider web with the domain specific explanation. In this MDO at least the mental health practice nurse, GP, social worker or community nurse are present. The patient is always invited. The outcome of this meeting is: (1) a personalised care plan; (2) appointment of one care coordinator and (3) a structured follow up plan (frequency and duration) of the progression of this patient's problems.
4. Execution of the personalised care plan. The care coordinator has frequent contact with the patient. A minimum of 3 consultations for the first 12 weeks is set, however more frequent consultation can be expected. The proactive nature of this contact is emphasized. A minimum of 4 consultations between patient and care coordinator is set. These minimum amount of consultation is deliberately set to take frequency of consultation as an outcome parameter. The proactive nature will be strongly endorsed, however implementation may differ according to the needs of each individual patient. Given the complex nature of the population the frequency of contact is expected to be higher in the majority.
5. Follow-up of the personalised care plan. During the regular monthly meetings of the health and social care network the follow-up of the patients will be reviewed. Each patient will be discussed at least two times, but more often if necessary. In case the care plan is not followed correctly or it does not have the desired outcome, the patient and the care network will make the needed adjustments to the care plan.

5. METHODS

5.1 Study parameters/endpoints

5.1.1 Main study parameter/endpoint

The main study parameter is incremental cost-effectiveness. To measure this outcome several data sources will be used and linked at the individual level.

Costs and utilisation of care during the trial

At the start of the study (t=0) and at the end (t=22) data on care usage and costs will be collected. Data on medical and acute care utilization for individual patients will be obtained from HIS and CBS microdata, supplemented with patient reported data. A selection of relevant (potential) costs for this population is made via expert opinion. The patient reported data consist only of data not available in HIS, for which questions were selected from the iPCQ, iMCQ and TiC-P questionnaires (See F1). Items with limited effect on cost of care which were not retrievable from HIS or microdata were excluded (See F1).

These data will be translated into cost using standard cost prices from the Dutch guideline for economic evaluations. The datasets containing coded data will be stored on the I-Drive of the LUMC for a period of 15 years. This drive is secured and only accessible by the researchers. Baseline characteristics from patients as well as information collected from the questionnaires will also be securely stored in an online database, named CASTOR.

Cost and utilisation of care previous to trial

The medical data from 3 years prior to the start of the study will be used to analyse the costs and utilisation of care. This extended period used for data analysis was deliberately chosen to include a timeframe during and before the SARS-CoV-2 pandemic. It is yet unknown how the pandemic and its subsequent measures affected our population and their usage of care.

Data on cost of care and care utilization prior to the start of the trial is retrieved from CBS microdata (Statistics Netherlands). Data from several sources are linked at a personal level by Statistics Netherlands in a secured remoted access environment. Data in the CBS microdata environment is secured by using a linkage key. All data in this environment is pseudonymized and data extraction is checked by Statistics Netherlands on traceability. By doing this, the privacy and linkage on individual level is secured. The proposed linkages in this proposal are in accordance with the General Data Protection Regulation (GDPR), as Statistics Netherlands is allowed by law to link data sets under strict disclosure condition (The European Parliament & the Council of the European Union, 2016).

Quality of life

The EQ-5D-L5 will be used to provide the quality of life measures in this study. This questionnaire is used to define health in terms of 5 dimensions: self-care, usual activities, mobility, anxiety/depression and pain/discomfort. It is also possible to define unique health states with this questionnaire, as each domain has five answer levels ranging from no problems to extreme problems (Versteegh et al., 2016). Besides being short and easy to comprehend, the questionnaire is also validated. In addition, quality of life will also be assessed by using the validated SF-12 (12-items), including 8 dimensions, namely: bodily

pain, vitality (energy and fatigue), general mental health (psychological distress and well-being), general health perceptions, limitations in physical activities because of health problems, limitations in social activities because of physical or emotional problems, limitations in usual role activities because of emotional problems, and limitations in usual role activities because of physical health problems (Turner-Bowker et al., 2014).

The 'cost and utilization and EQ-5D-L5 questionnaires will be filled in at 7 or 8 different timepoints, which will result in 7 or 8 measurements per participant. Participants are asked if they prefer a questionnaire on paper per post or one per email (using Castor). After receiving the questionnaire participants have one week to fill out the questionnaire. If there is no response, patients are called and offered an interview by phone on the questionnaire. The first interview will be done at the start of the study (t=0). Afterwards information for the questionnaires will be gathered 6 or 7 more times, see figure 1 in §3 study design for an overview and timing of questionnaires. In order to achieve more reliable results, a member of the research team will administer the SF-12 and other secondary study parameter questionnaires that might require extra guidance, during a face to face interview at three time points (before the start of the intervention, at the end of the intervention, and three months after the intervention has ended).

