All clusters start to collect control data at the same time ($t=0$). The 20 clusters will be divided into four groups evenly and each group will be randomly assigned one of four time points at which they will start to implement the proactive integrated care intervention. The first switch will be after 2 months ($t=2$). Every subsequent 2 months a next group of general practices will switch to the intervention mode until all groups have started the intervention. All groups will continue with the intervention as described in this protocol for a total of 12 months. After the 12 months of intervention, care will be delivered as usual. There is no objection if care providers and patients wish to maintain certain aspects of the intervention. All measurements and timepoints after the switch to the intervention falls under the intervention period. The total duration of this study comprises 22 months. This results in varying control period ranging from 2 to 8 months. The total of intervention and follow-up period vary from 14 to 20 months. This time table is summarized in the following chart.

In order to achieve more accurate answers from patients and in turn more reliable results, a member of the research team will administer the SF-12, and questionnaires on proactive coping (UPCC), and self-efficacy (PAM-13 and SE+IN) during a face to face interview, as these might require extra guidance when filling in. This will be done at three time points for each group (before the start of the intervention, at the end of the intervention, and two months after the intervention has ended).

[figure not shown]

Figure 1. This figure depicts the time schedule of this study. The EQ-5D-5L is administered 7 or 8 times, depending on cluster, and is depicted as a square. The Care and Work questionnaire is depicted with an arrow. The questionnaires PAM, SE+IN, SF-12 and UPCC are administered thrice: at the start and end of intervention and two months after ending the intervention (star). The dot represents the HCCQ and adapted NPS at 6 months after the start of the intervention. Focus groups (triangle) are organised per cluster, after finishing the intervention.

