- As part of process evaluation all involved professionals (GP, POH-GGZ, social workers or other) will be invited to join a focusgroup on their experience with this proactive, integrated care approach and the audio records of the intake and MDO will be scored on the level of shared decision making by two independent observers.
- Collection of data on: medical and acute care utilization, medical costs. (beginning and end of study).

The following time investment will be asked from each patient:

- 10 minutes: invitation of the patient by the GP practice and sharing of information about the study with the patient. Permission to send information about the study, will be asked.
- 10 minutes: follow-up with patient about participation in the study. If the patient agrees to participate, an informed consent form will be send out.
- 170 minutes for the questionnaires: this consists of 4 timepoints of EQ-5D-5L and Care and work questionnaire (4x10min = 40min), two timepoints of psychological questionnaires(SF-12, PAM-13, SE+IN) with EQ-5D-5L and care and work (2x40min = 80min), once EQ-5D-5L with Care and Work and evaluative questionnaire (modified NPS, HCCQ) (1x 10min = 10 min) and once psychological questionnaires combined with EQ-5D-5L (1x40min = 40min).
- 45 minutes: first consultation based on the Positive Health Methodology.
- 60 minutes (2x30=60min): all patients are invited and stimulated to join the multidisciplinary meetings. Patients will be discussed at least at least 2 times during the 12 month period. Additional ad hoc meeting is possible if necessary.
- 10-30 minutes (minimum of 4 times, thus combined total of 40-120 minutes): for the extra meetings that patients are going to have with their care coordinator, according to their personal care plan.
- 60 minutes: focus group focused on the patients their experience with the intervention. Each focus group will be 60 minutes and each patient will only be invited once. This will be done after they end the intervention.

	First three month period	Total 12 months period	Total in study period
POH-GGZ intake	1x45 min	1x 45 min	1x45 minutes
Multidisciplinary meeting	1x30 min	Minimum 2x 30	Minimum 2x 30 minutes
Care coordinator	Minimum of 3x, more frequent contact is	Minimum of 4x in 12 months, however more	Minimum of 4x in 12 months

	possible. Proactive nature of this contact is highlighted.	frequent contact is expected. Proactive nature of contact is highlighted.	
Questionnaires			170 minutes

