5.5 Replacement of individual subjects after withdrawal

Patients that chose to withdrawal from the study, will not be replaced.

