5.6 Follow-up of subjects withdrawn from treatment

When a participant chooses to retract from of the study, data collection for that participant will stop. The data collected until the moment of withdrawal will be used when analysing the data, unless the patient specifically requests otherwise.

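### Read literally, a participant who withdraws between t=0 and t=22 contributes no in-trial HIS or CBS costs, even for the months before withdrawal

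*Protocol*

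**What the plan says.** Section 5.1.1, under the costs during the trial, sets the timing: "At the start of the study (t=0) and at the end (t=22) data on care usage and costs will be collected". It names the sources in the next sentence: "Data on medical and acute care utilization for individual patients will be obtained from HIS and CBS microdata, supplemented with patient reported data". Section 5.3 repeats the timing in its list of procedures: "Collection of data on: medical and acute care utilization, medical costs. (beginning and end of study". The patient questionnaires have a restricted role: "The patient reported data consist only of data not available in HIS".

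Section 5.6 gives the withdrawal rule: "When a participant chooses to retract from of the study, data collection for that participant will stop". It continues: "The data collected until the moment of withdrawal will be used when analysing the data, unless the patient specifically requests otherwise". Section 5.5 adds: "Patients that chose to withdrawal from the study, will not be replaced".

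Three further points bear on this. Section 3 gives the length of the study: "The total duration of this study comprises 22 months". Section 4.4 plans 200 patients with 20% lost to follow-up. Section 6 promises intention-to-treat and per-protocol analyses.

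**The concern.** Each rule is reasonable alone. Two extractions are enough for routine data when everyone stays to the end, because the second can look back over the whole trial. Stopping collection at withdrawal while keeping what is already in hand is a common policy. Combined, they work against each other. At the moment a participant leaves, the only routine extraction already made is the one at t=0, which contains no care delivered during the trial. The look-back extraction at t=22 falls after withdrawal.

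Section 5.6 evidently means to preserve information from before withdrawal. For questionnaires it does so. For routine costs the timetable may leave nothing to preserve. Cost is one of the two components of the main study parameter, the sample size in section 4.4 rests on spending, and withdrawn patients are not replaced. If people who leave differ in their care use from those who stay, the cost difference could be biased. Control time is short, 2 to 8 months per patient, so losing a control period that a patient has completed is unwelcome. An analysis plan cannot recover data that were never extracted.

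**Working it through.** The plan states no figure on this point, so there is none to reproduce. The check sets the rules side by side and then illustrates the size.

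**Rules applied to a withdrawal at month 10**

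- Routine extraction at t=0 (5.1.1, 5.3): done, but it covers only care before the trial.
- Interim extraction, or extraction at withdrawal: none described in 5.1.1, 5.3 or 5.6.
- Routine extraction at t=22: falls after withdrawal, when under 5.6 collection for this participant has stopped.
- EQ-5D-5L and cost questionnaires completed by month 10: already collected, so kept under 5.6.
- Can questionnaire costs replace the HIS part? No, because 5.1.1 limits them to what HIS does not hold.

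On the literal reading, in-trial HIS and CBS costs for months 0 to 10 are therefore absent.

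**Inputs for the size**

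- N = 200 patients (4.4).
- Duration T = 22 months (section 3), so planned time is 200 × 22 = 4,400 patient-months.
- Share retracting, w: not in the protocol. Assumed to be 5%, 10% or 20%. The top value equals the whole loss to follow-up allowed for in 4.4.
- Withdrawal times: assumed uniform over 22 months, so the mean time in the study before withdrawal is 22/2 = 11 months.

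**Formulas**

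- Patients without in-trial routine costs = N × w.
- Missing on the literal reading = N × w × 22 / 4,400.
- Missing if months before withdrawal are kept = N × w × 11 / 4,400.
- Needless loss = the difference, N × w × 11 patient-months.

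| w | Patients | Missing, literal | Missing if earlier months kept | Needless loss |
|---|---|---|---|---|
| 5% | 10 | 220 (5%) | 110 (2.5%) | 110 (2.5%) |
| 10% | 20 | 440 (10%) | 220 (5%) | 220 (5%) |
| 20% | 40 | 880 (20%) | 440 (10%) | 440 (10%) |

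**Control time within that loss**

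For a control period of k months, the expected control time lived before a uniform withdrawal is k − k²/44. For k = 2, 4, 6 and 8 this gives 1.91, 3.64, 5.18 and 6.55, with mean 17.27/4 = 4.3 months. The mean control period is (2 + 4 + 6 + 8)/4 = 5 months. So, under these assumptions, the lost routine data include on average 4.3 of a withdrawn patient's 5 control months.

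**The case against.** The strongest reply is that the loss is inferred. HIS and CBS record care as it happens, and t=22 is only when the researchers draw the data. Section 5.6 may have been meant to cover care dated before withdrawal, whenever extracted. That is a fair reading, and it rules out saying that the protocol definitely discards these data. But 5.6 speaks of data collected, and 5.1.1 uses the same verb for what happens at t=0 and t=22. Anyone applying the words as written would not run the later extraction. The consent form might settle the matter. It is not available here, so its silence is not counted against the plan.

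A reader might also infer more than the text supports:

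- *That 40 patients will be lost and routine costs will exist for only 160.* The 20% in 4.4 is loss to follow-up, not a withdrawal rate. Section 5.6 applies when someone chooses to leave the study. Nothing in it bars the t=22 extraction for patients who merely stop answering questionnaires, and patients who return to usual care under 5.4.1 are not clearly caught.
- *That costs and QALYs rest on different patients.* Withdrawn patients keep questionnaire costs as well as EQ-5D-5L answers up to withdrawal. The restriction on questionnaires refers to HIS, not CBS, so some overlap with CBS items is possible. The item list is not shown.
- *That intention-to-treat is impossible for costs, or becomes a completers-only analysis.* Missing costs are a missing-data problem, and how they are handled may stand in an analysis plan that is not shown.

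Finally, stopping all collection at withdrawal is a legitimate policy. Asking about extraction beyond that date is an improvement on offer and does not repair the loss of earlier months.

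**Conclusion.** The point holds as a gap between two stated collection rules. Read literally, sections 5.1.1, 5.3 and 5.6 leave a participant who retracts between t=0 and t=22 without in-trial HIS or CBS costs, including for the months before withdrawal. No visible section makes an exception. This weakens the cost side of the intention-to-treat cost-utility analysis without making it impossible. Bias arises only if withdrawal is related to care use, which the documents do not show.

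The size is unknown because no withdrawal rate is given. Under uniform withdrawal, the needless loss ranges from 2.5% of planned patient-months at a 5% rate to 10% at a 20% rate. The top of that range is an upper bound under the protocol's own planning figure, since it treats every loss to follow-up as a formal retraction. The mechanism does not depend on the rate.

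**What to change.** In sections 5.6 and 5.1.1, state that:

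(a) for participants who withdraw, HIS and CBS use and costs from t=0 to the withdrawal date are still extracted, at withdrawal or at t=22, and analysed unless the patient objects;

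(b) at withdrawal the patient is asked separately whether passive HIS and CBS extraction may continue to t=22, which requires no further effort from the patient.

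Item (a) closes the gap. Item (b) is a further gain that also limits the loss after withdrawal. The patient information and consent wording should match, and should be in place before withdrawals occur.

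The cost is one paragraph, a line on the withdrawal form and a small amendment. No visits or patients are added. Some patients will refuse (b), and their months after withdrawal will stay missing.
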